### **Data Analysis**

We first discuss general issues and then turn to analyses specific to the aims of the proposed research.

**Missing Data.** In general, missing data is infrequent and not problematic, but occasions may arise where this must be formally addressed. Data can be missing at random (MAR), missing completely at random (MCAR) or missing in a systematic way. To gain perspective on the nature of the missingness for a given variable, we will create a dummy variable coded for each respondent: 1 = missing value on the variable or 0 = not missing. We will test for associations between this variable and others in the models. We also will apply Little's multivariate test for MCAR. Missing data also can result from attrition. We will differentiate these two sources of missingness and explore for each. We will use Full Information Maximum Likelihood (FIML) and multiple imputation (MI) or systematically model missing data bias, depending on the data and the models.

**Assumption Violations.** We will use bootstrapping to derive asymmetrical confidence intervals or robust methods to address assumption violations. Mplus offers algorithms for both. In general, we will be sensitive to assumption violations and explore data cautiously.

**Outliers.** We will apply standard methods for outlier detection (e.g., analysis of leverage statistics, residuals, and dfBetas) and also use graphical approaches.

**Multiple Items, Variables, and Contrasts.** For all of our multi-item measures, we will evaluate the coefficient alphas and factor structures to ensure they are consistent with their psychometric histories. We will examine the intercorrelations and the results of exploratory or confirmatory factor analyses to guide choices about combining indices or latent constructs. When we conduct multiple significance tests, we will compare the robustness of our conclusions both with and without statistical corrections for multiple tests using the strategy discussed in Jaccard & Guilamo-Ramos. In general, we will use a Holm adjusted modified Bonferroni method or the False Discovery Rate (FDR) method for controlling experiment-wise error, both of which are more powerful than Bonferroni methods.

**Specification Error.** We will be sensitive to issues of specification error, being careful to explore a wide range of model diagnostics to protect against gross model misspecification.

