**Traditional SEM Analyses.** Many of our analyses will use structural equation modeling (SEM). A useful computer program for analyzing complex SEM is Mplus. It offers bootstrapping, robust standard errors, and numerical strategies to deal with mixtures of categorical and continuous endogenous variables. The models tested will generally be statistically over-identified. We will evaluate model fit using both global indices (chi square, the Bollen-Stine bootstrapped chi square, GFI, CFI, standardized RMR, RMSEA, and p-value for the test of close fit) and focused indices of fit diagnostic of specific points of ill fit (standardized residuals for predicted minus observed variances and covariances, modification indices, the presence of offending estimates, etc.). We will compare results of traditional modeling (maximum likelihood) with those from robust standard errors and bootstrapping. We will have increased confidence in coefficients in results across analytic methods. In the face of poor fit, we will examine diagnostics for revising the model that, first and foremost, are conceptually meaningful. Analytic strategies for interaction effects in complex SEM models are somewhat controversial. Mplus offers a quasi-maximum likelihood method that has desirable properties when data are multivariately normally distributed. Marsh et al. suggest a simple strategy for non-normal data, but which should be supplemented with limited simulation analysis to ensure one is not led astray by relaxed model constraints. [name] is skilled at the analysis of interactions in structural equation models and has co-authored several books on the topic. The strategies in Mplus and suggested by Marsh et al. will be pursued as well as limited information estimation approaches using traditional regression models.

[figure not shown]
**Randomization Bias.** We will assess differences at baseline between the groups (PN vs. controls) on major demographic and background variables (e.g., sex, age, education), and if necessary, add these as covariates to the analyses. In our past studies, we have not found significant differences between the groups on these variables when our sample sizes are at the numbers we have proposed (>75 per cell).

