### **Specific issues and approaches for the analyses of the Specific Aims.**

**Aim 1: Evaluate the efficacy of PN intervention.** The primary focus of the analyses will document differences on our primary outcomes (alcohol use and alcohol-related harms) and secondary outcomes (marijuana use, nicotine use, and their combined use with alcohol) between the groups (PN/Control) using a mixed measures analysis of variance. A 2 X 3 (groups X time) MANCOVA will test the impact of the PN intervention on our outcome variables contrasting baseline tendencies against follow-up assessments (3 waves: baseline, 1 mo., and 6 mo.). For Aim 1 (analysis of efficacy), we will conduct an intent-to-treat analysis that will include all individuals who have been randomized to a condition. We will also examine differences in all outcomes by sex of the student (as a relevant biological variable), sexual orientation, and gender identity adding these as covariates to the analyses. We will be sensitive to inflated experiment-wise error rates and control these with modified Bonferroni methods.

**Aim 2: Examine mediators.** The second aim examines mediation paths in Figure 1 using SEM. We will follow the recommendations of MacKinnon (joint significance). For example, we will examine the relationship between the effects of the PN on predictors at the immediate post-PN assessment (1 mo. follow-up) and their subsequent effects on outcomes at the 6 month follow-up. The models will be statistically over-identified. We will examine global fit indices and focused indices of fit diagnostic of specific points of ill fit in the model (e.g., standardized residuals for predicted minus observed variances and covariances, and modification indices). We will use robust standard errors and bootstrapping. In the face of poor model fit, we will examine diagnostics that are conceptually meaningful and will significantly improve model fit.

[figure not shown]

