### **Multiple Trajectories that Covary.**

The analyses can be extended to identify multiple trajectories that covary over time and by group (PN/Controls; Figure 3). For example, the analytic approach would examine the changes over time in parental communication (PCOM) associated with the changes over time in alcohol use and include the effects of time-invariant covariate of PN (vs. controls). This growth curve can be expanded to include other constructs (e.g., parent communication). The focus is on trajectories of change over time rather than single variables. These analyses have not been done in any previous research examining brief PN efficacy or mediation processes in alcohol use but have been used

in other risky behavioral areas with good effect. This also can be modified for lagged effects and complex structural dynamics typically discussed in traditional panel analysis. It is possible to parameterize a growth curve model in traditional panel analysis terms like it is possible to parameterize traditional panel analysis in growth curve model terms. The mathematical details can be rather complex, and our experience is that typical social science readers are more comfortable with one framework or the other, depending on the research question. Our point is that for questions that pursue the analysis of the relationship between multiple trajectories, fairly complex causal dynamics and error structures can be modeled.

**Limitations/Alternative Strategies for Aim 2.** An alternative would be to recruit a school district or an adequate number of schools, randomly assigning schools to condition. This would not, however, produce a nationwide sample and would be costly in recruitment and tracking. Administration under these conditions is not, however, directly analogous to eventual dissemination. We accept this tradeoff for the advantages of a representative, national sample.

**Indicators of Success/Benchmarks.** One indicator of success will be if we hit initial, 1- and 6-month recruitment and retention targets. Secondly, we expect a high degree of fidelity (i.e., 80% accessing all required material and at least one optional section). The next indicator would be short term effects on mediators on the 1-month follow up. Finally, and most importantly, will be significant effects on behavioral outcomes with a successful test of the conceptual model in Figure 1.

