For Aim 2, we will use structural equation modeling (SEM) to assess paths between the Group (PN vs. Control) and the mediators (parent-child communication, parental monitoring, parental permissiveness) and student factors at follow-ups (e.g., motives, behavioral willingness, norms, expectancies) as described in MacKinnon et al. In terms of determining the proper sample, the use of SEM means that in addition to statistical power, issues of the stability of the covariance matrix, model complexity, and use of asymptotic theory must be taken into account. In terms of power, it is difficult to evaluate the power associated with specific path coefficients in complex SEM models due to the large number of assumptions about population parameters that must be made. A rough approximation can be obtained by applying power analyses for a coefficient in multiple regression analyses in the context of limited information estimation of path models. As an example, for a regression analysis with 5 predictors (e.g., intervention group, parent discussions, student motives, behavioral willingness, sex, and age) where the squared multiple correlation is 0.25 and where one wants to detect a predictor accounting for at least 5% unique variance in the outcome (e.g., alcohol misuse or alcohol-related consequences), the sample size to achieve power of 0.80 is approximately 125. For a logistic regression analysis having a dichotomous outcome (e.g., yes/no to heavy episodic drinking in past 30 days) where the target predictor is a continuous predictor (e.g., motives), with four other predictors in the equation (e.g., group, parent discussions, sex, and age), where the event rate at the mean of all predictors is 0.20 and where the multiple correlation of the predictor with the other predictors is 0.30, the sample size needed to detect an odds ratio of 1.75 expressed in standardized metrics is about 170 and for an odds ratio in standardized metrics of 2.00 is about 110. Our projected completed sample sizes exceed these thresholds. Thus, we should have sufficient power to evaluate Aim 2 for continuous and non-continuous outcomes.

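### Once the Aim 2 structural equation model is revised from its own fit diagnostics, its fit no longer tests Figure 1 and p-values for the searched paths are not nominal; the plan neither says so nor ties its success benchmark to the original model

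*Combined protocol and SAP*

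**What the plan says.** The Aim 2 paragraph under the analyses of the Specific Aims sets the method: "The second aim examines mediation paths in Figure 1 using SEM", with mediation judged by joint significance of the paths. It names the diagnostics to be inspected, "standardized residuals for predicted minus observed variances and covariances, and modification indices", and then gives the rule for a badly fitting model: "In the face of poor model fit, we will examine diagnostics that are conceptually meaningful and will significantly improve model fit".

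The Traditional SEM Analyses paragraph under Data Analysis states the purpose outright: "In the face of poor fit, we will examine diagnostics for revising the model that, first and foremost, are conceptually meaningful". That paragraph lists seven global fit measures (chi-square, its Bollen-Stine bootstrap version, GFI, CFI, standardized RMR, RMSEA and the test of close fit) without a threshold for any of them.

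Indicators of Success/Benchmarks puts one criterion above the rest: "Finally, and most importantly, will be significant effects on behavioral outcomes with a successful test of the conceptual model in Figure 1".

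On multiplicity, Data Analysis says that "we will compare the robustness of our conclusions both with and without statistical corrections for multiple tests". The modified Bonferroni sentence belongs to the Aim 1 paragraph. Neither deals with a search over model structures.

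I found no definition of poor fit or of a successful test, no list or limit of permitted changes, and no holdout sample. Nor did I find a statement of which model is reported first, or of how a revised model is to be labelled.

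**The concern.** A dataset that has suggested a change to a model cannot then confirm the changed model. Modification indices point to the omitted paths that would most improve fit in this sample. Adding them improves fit by construction, and the added paths tend to be significant because that is how they were chosen. If the success criterion is read on the revised model, a Figure 1 that the data rejected could be described as having passed its test.

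The stake is what the trial may conclude about mechanism. The Dissemination Plan lists a test of the mediation and moderation model as one of three main papers, and the Specific Aims make dissemination conditional on a successful evaluation. The mediators are labelled tertiary outcomes, so this does not touch the efficacy conclusion.

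**Working it through.** **1. The plan's own Aim 2 figures.** Statistical Design and Power gives about 125 participants for 80% power, "for a regression analysis with 5 predictors", with R² = 0.25 and 5% unique variance. (Six example predictors are listed.) Alpha is not stated for this calculation; I assume 0.05 two-sided.
- f² = 0.05 / (1 − 0.25) = 0.0667. With a noncentral F, 1 numerator df and λ = f²(u + v + 1), N = 124 for five predictors and 125 for six. The figure reproduces.
- Logistic case: N = (1.960 + 0.842)² / [P(1 − P)(ln OR)²] / (1 − 0.30²) with P = 0.20. For OR 1.75: 7.85 / (0.16 × 0.313) / 0.91 ≈ 172, against about 170 stated. For OR 2.00: 7.85 / (0.16 × 0.480) / 0.91 ≈ 112, against about 110 stated.

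These figures are sound for one coefficient in a model fixed beforehand. They say nothing about a model chosen by search.

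**2. Simulation set-up.** n = 280, the 6-month number expected in the retention section. Figure 1 is not shown, so the structure is assumed: PN → communication → four student factors (motives, expectancies, willingness, norms) → outcome, all observed. Seven variables give 7 × 8 / 2 = 28 variances and covariances. The model uses 1 + 1 + 4 + 4 paths and variances (PN variance, PN → communication, communication → factors, factors → outcome) plus 6 residual variances, 16 in all. That leaves 12 df and 12 omitted relations: 4 PN-to-factor, 1 PN-to-outcome, 1 communication-to-outcome and 6 between pairs of factors. The path with the largest modification index is added until chi-square p > 0.05. There were 2,000 runs per scenario and no true PN effect.

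**3. Results.**

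| Starting model | Passes chi-square before revision | After revision | Mediation declared before and after |
|---|---|---|---|
| Wrong: communication-to-outcome path omitted | 17% | 99.8% | 5.5%, unchanged |
| Wrong: correlation among student factors omitted | 0% | 99.6% | 5.6%, unchanged |

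**4. The added paths.** In 6,000 runs with a correct starting model, revision was triggered in 5.6%, which is 334 runs. In each, the first path added was truly null. On the same data 331 / 334 = 99% had p < 0.05; on an independent sample of the same size, 15 / 334 = 4.5%.

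**5. Reading.** Fit after revision hardly separates a right Figure 1 from a wrong one. The p-value of an added path reflects its selection. The joint-significance test of the paths specified at the outset kept its error rate, since the search could not alter the PN-to-communication path here.

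**The case against.** The strongest reply is that the plan does not license free editing. Both passages confine changes to conceptually meaningful ones and act only when fit is poor. The simulated search was unrestricted, so it is harsher than the text. That is fair, but the constraint is applied after the diagnostics have been seen and without a list of allowed changes, so it narrows the search and does not remove the selection. Robust standard errors and bootstrapping address distributional assumptions, not selection.

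Three stronger readings are tempting, and the documents do not support them.
- A reader might infer that the benchmark cannot fail. It also needs significant behavioral effects, which come from the Aim 1 intent-to-treat analysis, and joint significance still failed in about 95% of the null runs in the table.
- A reader might infer that all Aim 2 p-values are invalid. H4 (PN on parent communication) and H5 (communication on student factors) are stated in advance. If fit is adequate nothing is revised, and paths the search leaves alone were not shown to be distorted.
- A reader might put the risk at 1 − 0.95^k for k omitted paths, for example 1 − 0.95^12 = 46%. (In simulation, 47% of runs had at least one index above 3.84.) That assumes every such path is freed. The plan states no such rule, and a correct model triggered revision in only 5.6% of runs under a chi-square trigger.

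The documents also do not say that the changed model is the one reported; they are silent on it.

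A further objection limits the remedy. Refusing any inference from a revised model can mislead too. In a separate simulation at n = 280 with an omitted communication-to-outcome path and no true student-factor effects (assumed coefficients 0.3 to 0.4), the unrevised model gave at least one false factor-to-outcome path in 63–70% of runs. With the path included it was 19%, about what four tests at 5% give (1 − 0.95^4 = 0.185). This stands, and it is why both models should be shown.

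**Conclusion.** The concern holds in limited form. As written, the plan allows a poorly fitting model to be revised on the same data and leaves open which model the most important benchmark is judged on. After such a revision, global fit is close to uninformative about Figure 1: wrong models passed in 0–17% of runs before and over 99% after. P-values for paths added or changed by the search are not valid at nominal level. The efficacy analysis in Aim 1, and Aim 2 paths that the search does not alter, are not shown to be affected.

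The percentages rest on an assumed model, an unrestricted search and a chi-square trigger, and would change with the real Figure 1. The direction does not depend on those choices. How often revision would occur cannot be stated, because the plan sets no trigger: it was 5.6% of runs for a correct model and every run when correlation among the student factors was left out. The point should be settled before analysis, but it concerns tertiary outcomes.

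**What to change.** In the analysis plan:
- Write out the Figure 1 model in full before outcome data are seen, including which residual covariances are free, and state what counts as acceptable fit.
- Report the fit of that model and its H4, H5 and joint-significance results first, whatever the fit.
- State that the benchmark's successful test of the conceptual model is judged on that model.
- Report any revised model beside it as exploratory. List every change with its reason, and show whether the H4, H5 and mediation conclusions differ between the two models.
- Treat paths added by the search as hypothesis-generating.

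The cost is some wording and one extra table. No more participants are needed and Aim 1 is unchanged. The downside is that the paper may have to say that the a priori model fits poorly, and where it does, the comparison of the two models has to carry the interpretation.

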### **Multiple Trajectories that Covary.**

The analyses can be extended to identify multiple trajectories that covary over time and by group (PN/Controls; Figure 3). For example, the analytic approach would examine the changes over time in parental communication (PCOM) associated with the changes over time in alcohol use and include the effects of time-invariant covariate of PN (vs. controls). This growth curve can be expanded to include other constructs (e.g., parent communication). The focus is on trajectories of change over time rather than single variables. These analyses have not been done in any previous research examining brief PN efficacy or mediation processes in alcohol use but have been used

in other risky behavioral areas with good effect. This also can be modified for lagged effects and complex structural dynamics typically discussed in traditional panel analysis. It is possible to parameterize a growth curve model in traditional panel analysis terms like it is possible to parameterize traditional panel analysis in growth curve model terms. The mathematical details can be rather complex, and our experience is that typical social science readers are more comfortable with one framework or the other, depending on the research question. Our point is that for questions that pursue the analysis of the relationship between multiple trajectories, fairly complex causal dynamics and error structures can be modeled.

**Limitations/Alternative Strategies for Aim 2.** An alternative would be to recruit a school district or an adequate number of schools, randomly assigning schools to condition. This would not, however, produce a nationwide sample and would be costly in recruitment and tracking. Administration under these conditions is not, however, directly analogous to eventual dissemination. We accept this tradeoff for the advantages of a representative, national sample.

**Indicators of Success/Benchmarks.** One indicator of success will be if we hit initial, 1- and 6-month recruitment and retention targets. Secondly, we expect a high degree of fidelity (i.e., 80% accessing all required material and at least one optional section). The next indicator would be short term effects on mediators on the 1-month follow up. Finally, and most importantly, will be significant effects on behavioral outcomes with a successful test of the conceptual model in Figure 1.

### **Objective 3: Finalize programming (if needed) and prepare materials for dissemination.**

We have budgeted for changes to PN based on the overall findings of the study. This may include any technological obstacles we face along with preparing for distribution across platforms and formats. Next, we will integrate PN into the RP website and Facebook sites for dissemination purposes. Finally, we will coordinate with D.A.R.E to integrate PN into its dissemination materials. It is anticipated that we will roll out PN at the annual D.A.R.E International Training Conference. We will also meet with our 4-H collaborators to discuss adoption in their Health Living program. We also will reach out to our other current partners, the Merck foundation, with whom we are expanding the reach of our HPV vaccination intervention and Planned Parenthood, through whom the intervention is currently disseminated. No funds will be used for marketing. This is discussed in further detail in the Commercialization Plan.

**Overall Phase II Limitations.** We accept that the methodology used is not directly representative of how PN will be ultimately implemented and this will require some adaptation to our community partners. Adaptation occurs in each instance of collaboration. For example, we branded (logos, terminology) our media literacy intervention as REAL messages for D.A.R.E. and as REAL messages for 4-H clubs. It also is possible GfK will be unsuccessful in recruitment and retention, although their record indicates otherwise. Finally, the duration of Phase II funding limits the length of follow up (e.g., no 1-year follow-up posttest) and the number of treatment conditions (i.e., no comparison to handbook version).

